5.1. Descriptions of Analysis Datasets

For purposes of analysis, Parts A, B, and C of the study will be analysed separately as the data for each becomes available. The table below defines subject populations which are defined primarily by participation and data creation in the applicable part of the study. When change from baseline is assessed, patients will be included in the analysis only if both a baseline and at least 1 valid post-baseline measure are available.

Population	Description
Randomized Population	Subjects from Part A randomized to receive on-site assessments first or remote assessment first.
Part A: Video Assessment	Randomized subjects that provide at least 1 pair (on-site and remote) of complete clinical assessments from Part A. Population will be scale-dependent.
Part B: Safety Population	Subjects who are dosed with donanemab during Part B.
Part C: Imaging and Clinical Follow-up	Subject who provide clinical and/or imaging data from Visit 201.

5.2. Patient Disposition

The protocol for this study makes the distinction between patient withdrawal from study and patient discontinuation of study treatment. Patient withdrawal occurs when a patient will no longer participate in the study (no longer taking study treatment and no longer being assessed). Patient discontinuation of study treatment occurs when a patient agrees to continue being assessed but will no longer take study treatments. Patient disposition summarizes the reasons for patient withdrawal from study and patient discontinuation of study treatment.

The percentage of patients withdrawing from study and discontinuing treatment across all parts of the study will be summarized.

5.3. Interim Analyses

Study AACH is an open-label study, with no study drug treatment during Parts A and C, and donanemab treatment during Part B. No interim analyses are planned for this study. Parts A, B, and C will be analysed as subjects complete those parts of the study and data becomes available. Treatment is unblinded in this study and data is available for sponsor use on a continual basis.

6. Part A Analyses

6.1. General Considerations

Statistical analyses of this study will be the responsibility of the sponsor or its designee.

Unless otherwise noted, statistical tests will be conducted at a 2-sided alpha level of 0.05 and 95% confidence intervals will be displayed as 2-sided.

No adjustments for multiple comparisons are planned.

All analyses involving calculation of ICCs will be limited to the Part A: Video Assessment population, requiring participants to contribute complete pairs of on-site and remote clinical assessments to be included. The ICC will be calculated as 2-way mixed-effect model looking for absolute agreement across raters, with raters defined as on-site assessment and VTC assessment.

A database lock is expected to occur after all randomized participants have completed participation in Part A of the study. Analyses related to the validation of remote assessments compared to on-site assessments will be conducted. As no study drug is administered during Part A, safety analyses will be limited.

Additional exploratory analyses of the data will be conducted as deemed appropriate.

6.2. Adjustments for Covariates

Models for each of the clinical endpoints are specified in the relevant sections below.

6.3. Handling of Dropouts or Missing Data

Because the ICC computation requires a complete on-site assessment and a complete virtual assessment, no imputation of missing values will occur in efficacy analyses for Part A. If any of the individual items for any scale are missing or unknown, the total score for that scale will be considered missing.

Whether virtual administration of the clinical assessments will result in more missing item scores relative to the on-site assessment is of interest. To address this question, the number of scale assessments with missing values for each of the clinical scales will be summarized by modality.

6.4. Baseline Demographics

Baseline demographics, clinical rating scales, disease characteristics, select concomitant medications, and imaging parameters will be summarized for the Part A: Video Assessment population.

6.5. Primary Objective

The primary objective of Part A of this study is to evaluate the reliability of VTC compared with on-site administered cognitive and functional measures. This will be assessed by estimating the intra-class correlation (ICC) and the associated 95% confidence interval for the first pair of

observations from participants and comparing the lower bound of the confidence interval to 0.70, the ICC cut-off for acceptable reliability.

Using the guidelines and notation for defining ICCs published by McGraw and Wong (1996), the ICC of primary interest for this study is a 2-way mixed model, interaction absent, with single measurements from each modality on participants, looking at absolute agreement – ICC(A,1). In the present study, the ‘raters’ are the two modalities by which the clinical scales are assessed, on-site and VTC. As we are interested in comparing these specific modalities, modality is considered a fixed effect.

For ADAS-Cog₁₃ total score, ADCS-ADL total score, iADRS total score, CDR Sum of Boxes, and MMSE total score, individual mixed models will be fit to the data with fixed effects of modality, time effect, age, years of education, and presence/absence of anti-dementia drugs and a random effect for subject. ICCs will be estimated using the mean squares from these models and defined as:

Absolute Agreement: $ICC (A,1) = (MS_{subj} - MS_{error}) / (MS_{subj} + MS_{error} + 1/n(MS_{modality} - MS_{error}))$

Consistency: $ICC (C,1) = (MS_{subj} - MS_{error}) / (MS_{subj} + MS_{error})$

95% Confidence intervals for these quantities will be constructed as specified in Table 7 of McGraw and Wong (1996).

Similar analyses will also be conducted for pairs 2 and 3 of each of the clinical outcomes specified above. As the number of subjects contributing additional pairs may be limited, no specific hypothesis/test is specified.

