### 9.2. Sample Size Determination

Approximately 200 participants will be enrolled and randomized in a 1:1 ratio to the 2 groups (Group 1: Cognitive/functional scale assessment on-site, followed by VTC assessment; or Group 2: Cognitive/functional scale assessment by VTC, followed by assessment on-site). It is expected that approximately 180 participants will complete Pair 1 of Part A. Approximately 150 participants are expected to complete the study.

A correlation coefficient of 0.80 between on-site and VTC assessment is assumed.

Furthermore, it is assumed that the 2 modalities will yield similar means but different standard deviations. A mean ADAS-Cog13 total score of 27.2 and a SD of 8 and 9 were used for the power calculation. These estimates were derived from Studies I8D-MC-AZES, I8D-MC-AZET, and H8A-MC-LZAX, all reflecting an early or mild AD population.

This sample size will provide approximately 81% power to demonstrate 'acceptable' reliability, defined as the lower limit of the 95% confidence interval for ICC above 0.70.

This power calculation is based on the ADAS-Cog13, as this is the scale anticipated to have most scale adaptations and most variability from on-site to VTC assessment. Other scales should therefore demonstrate equal or greater power for these comparisons.

Simulations (carried out in R) with 1000 iterations, utilizing above described assumption, yields an average ICC of 0.793 and average 95% confidence interval of 0.732 to 0.841.

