#### **9.4.2. Primary Endpoint(s)**

##### **Part A**

The primary objective for Part A of this study is to evaluate the reliability of VTC compared with on-site administered cognitive and functional measures. This will be assessed by estimating the ICC and the associated 95% confidence interval for the first pair of observations from participants and comparing the lower bound of the confidence interval to 0.70, the ICC cut-off for acceptable reliability.

Using the guidelines and notation for defining ICCs published by McGraw and Wong (1996), the ICC of primary interest for this study is a 2-way mixed model, interaction absent, with single measurements from each modality on participants, looking at absolute agreement – ICC(A,1). In the present study, the ‘raters’ are the 2 modalities by which the clinical scales are assessed, on-site and VTC. As we are interested in comparing these specific modalities, modality is considered a fixed effect.

An ANOVA model will be fit to the data with fixed effects of modality, time effect, age, years of education, and presence/absence of anti-dementia drugs. To estimate the ICC and the associated confidence interval, the appropriate mean squares from this model will be used for these estimates. Refer to the SAP for more details.

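### The Part A primary ICC is planned as a covariate-adjusted quantity, but the 0.70 cut-off and the 81% power fit an unadjusted one

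*SAP*

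**What the plan says.** SAP 6.5 fits one mixed model per scale with "fixed effects of modality, time effect, age, years of education, and presence/absence of anti-dementia drugs and a random effect for subject". It then states that "ICCs will be estimated using the mean squares from these models and defined as" ratios of MS_subj, MS_error and MS_modality, and that "95% Confidence intervals for these quantities will be constructed as specified in Table 7" of its cited methods paper. It does not say whether MS_subj is taken before or after the covariates, or which degrees of freedom go with it.

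Protocol 9.4.2 (Part A) is looser: "An ANOVA model will be fit to the data with fixed effects of modality, time effect, age, years of education" and anti-dementia-drug status. It names no subject term, says that "the appropriate mean squares from this model will be used for these estimates", and refers to the SAP. Both documents judge each scale by whether the lower 95% limit for Pair 1 exceeds 0.70.

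Protocol 9.2 bases power on ADAS-Cog13, with correlation 0.80, similar means, SDs of 8 and 9, and about 180 participants completing Pair 1. It says: "This sample size will provide approximately 81% power to demonstrate 'acceptable' reliability". Of the method it says: "Simulations (carried out in R) with 1000 iterations, utilizing above described assumption", which "yields an average ICC of 0.793 and average 95% confidence interval of 0.732 to 0.841". No covariate and no R² appear among the assumptions.

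**The concern.** An ICC is the share of total variance that lies between participants. Age and years of education do not change over the 4 weeks between the two visits of a pair, and drug status rarely does, so these covariates can explain only differences between participants. Fitting them beside a random subject effect takes that explained variance out of the subject mean square and leaves MS_error unchanged. The result answers a narrower question: how well the two modalities agree in ranking participants of the same age, education and drug status.

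That quantity is legitimate, but it is stricter. The 0.70 threshold is not restated for it, and the power statement does not mention it. What is at stake is a scale failing the Part A primary criterion although it would have met it on the ICC that was powered. Protocol 9.2 expects the other scales to have equal or greater power than ADAS-Cog13, so the gap carries over to them.

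**Working it through.** **Inputs.** From protocol 9.2: n = 180 pairs, r = 0.80, SDs 8 and 9, equal means (27.2), success if the lower two-sided 95% limit exceeds 0.70. Not in the documents, hence assumed: the share s of between-participant variance explained by the three covariates, taken as 0, 2, 5 and 10%. Drug status is treated as constant within a pair.

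**Step 1: expected mean squares without covariates.**
- Covariance = 0.80 × 8 × 9 = 57.6
- Mean variance = (64 + 81)/2 = 72.5
- E(MS_subj) = 72.5 + 57.6 = 130.1
- E(MS_error) = 72.5 − 57.6 = 14.9
- ICC = (130.1 − 14.9)/(130.1 + 14.9) = 115.2/145.0 = 0.794

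**Step 2: reproduce the plan.** 10,000 simulated trials with no covariates used two-way mean squares and F-based limits for ICC(A,1). They gave mean ICC 0.793, mean interval 0.732 to 0.841, and power 82.5%. The ICC and interval match protocol 9.2 exactly, and the power is within 2 points of 81%. With 200 pairs the interval is 0.735 to 0.839 and power is 86%, so the stated figures rest on 180 pairs. The simulation weights the modality term by 2/n where SAP 6.5 prints 1/n. With equal means that term has expectation zero, so the weight does not matter here.

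**Step 3: adjusted ICC.** Taking MS_subj after the covariates lowers its expectation by 2 × 57.6 × s, so the population value is

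ICC_adj = 57.6(1 − s)/(72.5 − 57.6s)

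At s = 5%, for example, this is 54.72/69.62 = 0.786.

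| Assumed share s | Population ICC_adj | Power, adjusted ICC | Power, unadjusted ICC | Same data: unadjusted passes, adjusted fails |
|---|---|---|---|---|
| 0% | 0.794 | about 82% | 82–83% | 1.0% |
| 2% | 0.791 | about 79% | 82–83% | 4.2% |
| 5% | 0.786 | about 74% | 82–83% | 9.9% |
| 10% | 0.777 | about 62% | 82–83% | 20.8% |

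Separate simulations agree on the adjusted power within about 2 points.

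**Step 4: size against simulation noise.** The standard error of an 81% estimate from 1000 iterations is √(0.81 × 0.19/1000) = 0.0124, or 1.2 points. The drop at s = 2% is about 3 points, and at 5% about 8.

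**Step 5: false validation.** With a true unadjusted ICC of exactly 0.70, the unadjusted analysis passes in 2.0–2.5% of trials. The adjusted one passes in 1.7, 1.2 and 0.4% at s = 2, 5 and 10%.

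**Step 6: degrees of freedom.** Using n − 1 instead of the covariate-adjusted value in the interval changes power by only 0.3–0.6 points.

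**The case against.** The strongest reply is that the loss depends entirely on an R² that the documents do not give. Nothing in them shows that age, education and drug use explain 5% or more of ADAS-Cog13 variance in this population. A figure given as approximate is just as sensitive to other inputs: without covariates, lowering the assumed correlation from 0.80 to 0.79 takes power from about 82% to 72%, and a 1-point mean shift takes it to 74%. The direction is also conservative, and the ICC and its interval are reported whatever the verdict. All of this stands and limits the weight of the point.

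A reader might infer more than the text supports, in three ways:

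- **That the SAP leaves two equally open readings, so the verdict is arbitrary.** If subject were fitted before the covariates, terms constant within a participant would change nothing. But then the SAP would list three covariates that do no work. A random subject effect beside participant-level fixed effects points to the adjusted mean square.
- **That degrees of freedom and the coding visit for drug status are material gaps.** The first is worth under 1 point of power, and the interval method is delegated to the cited table. On the second, Part A inclusion criterion 6 requires stable medication for at least 30 days before randomization. Protocol 6.5.1 permits changes when medically indicated, but few would fall within one pair.
- **That the protocol's simulation certainly omitted covariates.** The planned model with covariates that explain nothing gives the same figures. The 0.80 could also have been meant as an adjusted correlation, although pairing it with total-score SDs makes that less natural.

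The reply does not remove the mismatch itself. The planned model yields a conditional ICC, and neither the threshold nor the power statement is tied to it.

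**Conclusion.** The point holds as a mismatch between the planned estimate and the powered one. On its natural reading SAP 6.5 tests a covariate-adjusted ICC against 0.70, while protocol 9.2's figures are those of an unadjusted ICC on 180 pairs. It would go too far to say that 81% is wrong. It reproduces for the unadjusted ICC and is simply unsupported for the adjusted one.

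Under the protocol 9.2 inputs, the cost is negligible up to an assumed share of about 2% and clear from about 5%. The error runs one way: a scale may be failed that would pass on the powered ICC, and false validation does not rise. The point is worth correcting because it concerns a pass/fail primary endpoint and the correction is cheap. Confidence is moderate, because the size depends on the unknown R².

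**What to change.** **Preferred.** In SAP 6.5, compute the primary ICC(A,1) and its interval from subject, modality and time only, and report the covariate-adjusted ICC beside it as a labelled sensitivity analysis. This matches the power statement and needs no new data.

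The downside is that it changes a prespecified primary model in the favourable direction, in a study where SAP 5.3 gives the sponsor continual access to data. So document the change and its reason in the SAP and clinical study report. Decide under protocol 9.4.1 whether it alters a principal feature and needs an amendment. Date the change before any Part A ICC is computed, and report both ICCs. If Part A ICCs already exist, which the documents do not say, keep both in the report and label the covariate-free one as chosen afterwards.

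**Alternative.** Keep the covariates. State in SAP 6.5 that MS_subj is the covariate-adjusted subject mean square, and give its degrees of freedom. State that the 81% applies to the unadjusted ICC, and show power for the adjusted ICC over a stated R² range. This costs a few sentences and one rerun of the existing simulation.

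Either way, use one model description in both documents, since protocol 9.4.2 describes an ANOVA without a subject term and the SAP a mixed model with one.

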### 9.4.4. Tertiary/Exploratory Endpoint(s)

As a sensitivity analysis for the primary endpoint of Part A, to assess whether the VTC clinical assessment includes any bias relative to the on-site clinical assessment, an ICC looking at the consistency of the 2 measures will be calculated – ICC(C,1) per McGraw and Wong (1996). By definition, the consistency ICC will be equal to or larger than the ICC for absolute agreement. Large differences between the absolute agreement and consistency ICCs suggest a shift (upward or downward) in the VTC relative to the on-site assessment.

Using the same ANOVA model specified in Section 9.4.2, the ICCs and 95% confidence intervals for the second pair and third pair of on-site and remote clinical assessments will be estimated. Comparisons between the ICCs from the first pair of assessments and the second and third pairs of assessments will be made to measure consistency across measures. If fewer than 50 pairs of clinical assessments are collected for Pairs 2 or 3, only descriptive statistics will be reported. See the SAP for further details.

To compare disease progression as measured by VTC versus on-site, an MMRM will be fit to the clinical assessment measures. Observations will be grouped by test modality (VTC and on-site).

The MMRM will include terms for modality, visit, visit-by-modality interaction, age, years of education, and presence/absence of anti-dementia drugs. Visit will be considered a categorical variable. The null hypothesis is that the contrast between the VTC modality versus the on-site modality at each visit equals 0. An unstructured covariance matrix will be used to model the within-subject variance-covariance errors. If the unstructured covariance structure matrix results in a lack of convergence, the following tests will be used in sequence:

- heterogeneous Toeplitz covariance structure
- heterogeneous autoregressive covariance structure
- heterogeneous compound symmetry covariance structure
- compound symmetry covariance structure

The Kenward-Roger approximation will be used to estimate the denominator degrees of freedom.

Changes in the blood-based biomarkers of NfL, P-tau, and A $\beta$  during Part B will be summarized with observed case analyses.

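### The SAP's ICC(A,1) formula weights the modality term by 1/n where two modalities require 2/n, so it counts only half of any VTC shift and overstates absolute agreement

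*SAP*

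**What the plan says.** SAP section 6.5 (Primary Objective) states that "the ‘raters’ are the two modalities by which the clinical scales are assessed, on-site and VTC", so there are exactly two. The index is a two-way mixed-model ICC with "single measurements from each modality on participants, looking at absolute agreement – ICC(A,1"). It is to be computed from mean squares as "MS_{subj} - MS_{error}) / (MS_{subj} + MS_{error} + 1/n(MS_{modality} - MS_{error". The SAP does not define n. Protocol section 9.4.2 names the same index and leaves the detail to the SAP.

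The interval is specified separately, by reference to the cited ICC paper: "95% Confidence intervals for these quantities will be constructed as specified in Table 7". SAP section 6.1 sets two-sided 95% limits. Success in protocol section 9.2 is "defined as the lower limit of the 95% confidence interval for ICC above 0.70". The planning basis there is a correlation of 0.80, SDs of 8 and 9, and similar means for the two modalities. On numbers, "It is expected that approximately 180 participants will complete Pair 1 of Part A".

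Protocol section 9.4.4 adds the consistency ICC as a check for bias: "Large differences between the absolute agreement and consistency ICCs suggest a shift (upward or downward) in the VTC relative to the on-site assessment".

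**The concern.** Absolute agreement differs from consistency in one respect: it penalises a systematic difference between modalities. That penalty sits entirely in the modality term. If its weight is half what it should be, the reported primary estimate is too high for every scale where VTC and on-site scores really differ. The difference between the two ICCs, meant to reveal such a shift, also looks about half as large as it is.

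The error favours the conclusion the study hopes to reach. The planning simulation cannot expose it, because that simulation assumes no shift.

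**Working it through.** **Inputs.** k = 2 modalities (SAP 6.5). n = 180 pairs, SDs 8 and 9, correlation 0.80, similar means (protocol 9.2). The documents give no ADAS-Cog shift in points, so d below is an assumption and a range is shown. The calculation uses the plain two-way layout without the model's covariates.

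**Step 1: the plan's own figures.** I simulated 100,000 trials with n = 180 and no shift, using the standard F-based interval with Satterthwaite degrees of freedom (an assumption about the cited table). The average ICC was 0.793, the average 95% interval 0.732 to 0.842, and power 82.6%. The protocol states 0.793, 0.732 to 0.841, and about 81%, so the figures reproduce. The 1/n and 2/n weights give the same results here, so these figures cannot show which weight was used.

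**Step 2: the weight.** With k = 2:

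- subject variance = (MS_subj − MS_error)/2
- modality variance = (MS_modality − MS_error)/n
- error variance = MS_error

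Absolute agreement is the first divided by the sum of all three. Multiplying top and bottom by 2 gives

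(MS_subj − MS_error) / (MS_subj + MS_error + (2/n)(MS_modality − MS_error)).

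The coefficient 1 on MS_error in the denominator is k − 1 with k = 2. The SAP has therefore substituted k there but not in the modality term, where k/n becomes 2/n.

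**Step 3: what each weight does to a shift.** For a mean shift d, E(MS_modality) = E(MS_error) + n·d²/2. The 2/n term then has expectation d², and the 1/n term d²/2.

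**Step 4: a check that needs no variance-component convention.** Take 1 minus the mean squared VTC-minus-on-site difference, divided by the value that difference would have for unrelated scores with the same means and SDs.

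- Planning values, d = 4: the mean squared difference is 64 + 81 − 115.2 + 16 = 45.8. For unrelated scores it is 145 + 16 = 161. The result is 1 − 45.8/161 = 0.716, which is the 2/n value.
- Noise-free case, VTC = on-site + 5, between-participant variance 62.5: 1 − 25/150 = 0.833. The 2/n form gives 125/(125 + 25) = 0.833. The SAP form gives 125/(125 + 12.5) = 0.909.

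**Step 5: size at the planning values.** Covariance = 0.80 × 8 × 9 = 57.6 and mean variance = (64 + 81)/2 = 72.5. So E(MS_subj) = 130.1 and E(MS_error) = 14.9, with difference 115.2 and sum 145. The two indices are 115.2/(145 + d²) with 2/n and 115.2/(145 + d²/2) with 1/n. The consistency ICC is 115.2/145 = 0.794. The last two columns give consistency minus absolute agreement.

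| Shift d (points) | ICC, 2/n | ICC, 1/n (SAP) | Gap, 2/n | Gap, 1/n |
|---|---|---|---|---|
| 0 | 0.794 | 0.794 | 0 | 0 |
| 2 | 0.773 | 0.784 | 0.021 | 0.011 |
| 3 | 0.748 | 0.771 | 0.046 | 0.024 |
| 4 | 0.716 | 0.753 | 0.079 | 0.042 |
| 5 | 0.678 | 0.731 | 0.117 | 0.063 |
| 6 | 0.636 | 0.707 | 0.158 | 0.088 |

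The index equals 0.70 when the shift term is 115.2/0.70 − 145 = 19.57. That is d = √19.57 = 4.42 with 2/n and d = √(2 × 19.57) = 6.26 with 1/n. In 4,000 simulated trials at d = 5, the **point estimate** exceeded 0.70 in 26% with 2/n and 84% with 1/n. This is not the trial's success criterion.

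**Step 6: the success criterion.** Under the standard F-based interval, the weight enters the lower limit only through the degrees of freedom. Mean lower limits were 0.667 (2/n) and 0.666 (1/n) at d = 2, and 0.365 and 0.355 at d = 4. The pass rate was about 27% under either weight at d = 2, and 0% under either at d = 4 or more.

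**The case against.** The strongest reply is that success is judged on the lower confidence limit, which the SAP takes from the cited paper and not from the printed formula. This stands on the assumption in Step 6: the decision barely moves, and 1/n is if anything marginally stricter. The decision would be affected only if limits were built for the printed quantity itself, for instance by bootstrap, which the SAP does not propose.

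Second, large shifts may be unlikely. The protocol plans on similar means, and its section 2.2.2 reports two studies with no ADAS-Cog difference and a shift of a tenth of an SD for certain tasks. A tenth of an SD is 0.8 to 0.9 points here; at 0.85 points the ICC is 0.791 with 2/n and 0.793 with 1/n, a trivial difference. But the same section cites VTC overstating impairment in more impaired patients, without a size, and section 9.2 expects ADAS-Cog to need the most adaptation. An agreement index should not rely on the shift being small.

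Third, modality is fixed, and defining the spread of two fixed values with divisor 2 instead of 1 would give the printed formula (62.5/68.75 = 0.909 in the noise-free case). The SAP states no such definition, and Step 4, which uses no divisor, supports 2/n.

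Fourth, SAP section 6.6 tests the modality contrast at each visit directly, and the protocol sets no numerical threshold for a large gap between ICCs. Both points are true, so shift detection does not rest on the gap alone. They do not make the primary estimate correct.

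**Conclusion.** The concern holds. For two modalities and n paired participants, the printed formula gives a systematic shift half its proper weight. It overstates absolute agreement whenever MS_modality exceeds MS_error, and with no shift the two weights agree in expectation.

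At the planning values the overstatement is 0.011 at a 2-point shift, 0.037 at 4 points (0.753 against 0.716) and 0.054 at 5 points (0.731 against 0.678). The same formula serves every scale and is carried over to Pairs 2 and 3.

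What is affected is the reported primary estimate, its coherence with its own confidence interval, and the absolute-versus-consistency comparison. The pass/fail result is essentially unaffected if the cited limits are the standard F-based ones. The sizes rest on the protocol's SDs and correlation and on assumed shifts; the halving itself is algebra. It takes n to be the number of pairs. If n meant total observations, the under-weighting would be worse.

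**What to change.** In SAP section 6.5, replace 1/n with 2/n in the ICC(A,1) formula. Define n as the number of participants with a complete pair for the scale and pair being analysed. State that the estimate and its limits are computed from the same mean squares. Check the signed SAP and the analysis program to see which weight was actually coded.

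The cost is one character in the SAP and the matching line of code, with no change to design, data or sample size. If VTC and on-site means differ, the reported ICC will be somewhat lower.

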### **2.2.2. Video Assessment**

VTC in healthcare settings is common and is used to carry out cognitive assessments, to conduct psychiatric interviews and consultations, and to help with the management of chronic conditions (Cullum et al. 2014; Ignatowicz et al. 2019). Research comparing clinical interviewing conducted through video conferencing and traditional on-site conditions indicates generally good agreement in a variety of conditions, including dementia and cognitive impairment of various causes (Castanho et al. 2017).

A recent systematic review and meta-analysis assessed the effect of VTC administration on adult cognitive tests and investigated whether the scores acquired during a VTC administration were different from those acquired during on-site administration (Bearly 2017). The review concluded that studies including participants with a mean age of 65 to 75, as well as studies that utilized a high-speed network connection, indicated consistent performance across VTC and on-site conditions (studies with slower connections were more variable). Furthermore, subgroup analyses indicated that VTC scores for untimed tasks and those allowing for repetition fell 1/10th of a standard deviation below on-site scores. Test-specific analyses indicated that verbally mediated tasks were not affected by VTC administration but tasks with a motor component yielded more variable data.

With specific regard to instruments that are often used in AD clinical trials, the feasibility of the MMSE by VTC in an older population with dementia has been investigated by several authors (Ciemins et al. 2009; Cullum et al. 2014; Castanho et al 2017) and no differences were reported between video and on-site administrations.

VTC of the ADAS-Cog13 has not been investigated as often as the MMSE. Results from 2 studies show no difference in baseline and follow-up scores of the ADAS-Cog13 between on-site and VTC testing (Carotenuto et al. 2018; Yoshida et al. 2020). One of these studies reported that in patients with more pronounced cognitive deficits (MMSE <17), the assessment via VTC overestimated the cognitive impairment (Carotenuto et al. 2018).

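### The tabled interval for ICC(A,1) appears too wide for a fixed two-level modality once VTC scores shift moderately (about 0.2 SD or more), so Part A can reject a scale that agrees acceptably

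*SAP*

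**What the plan says.** SAP 6.5 assesses Part A by estimating ICC(A,1) on the first pair and "comparing the lower bound of the confidence interval to 0.70, the ICC cut-off for acceptable reliability". SAP 6.1 makes the interval 95% and two-sided. The raters are "the two modalities by which the clinical scales are assessed", and the SAP is explicit about their status: "As we are interested in comparing these specific modalities, modality is considered a fixed effect". For the interval, the SAP refers outside itself: "95% Confidence intervals for these quantities will be constructed as specified in Table 7" of the cited paper. Neither document prints the interval formula. Protocol 9.4.2 says that the estimate and its interval both come from the model's mean squares.

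The power statement in Protocol 9.2 uses ADAS-Cog13, correlation 0.80, SDs of 8 and 9 and about 180 completed first pairs, and "it is assumed that the 2 modalities will yield similar means but different standard deviations". It reports about 81% power, with an average ICC of 0.793 and an average interval of 0.732 to 0.841. The only shift size in either document is in Protocol 2.2.2, where a meta-analysis found that "VTC scores for untimed tasks and those allowing for repetition fell 1/10th of a standard deviation below on-site scores".

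**The concern.** With two modalities, the modality mean square has 1 degree of freedom. The standard interval for ICC(A,1) combines it with the error mean square by a Satterthwaite approximation. As the shift grows, the 1-df term takes over, the effective degrees of freedom fall, and the lower limit drops. That behaviour suits modalities sampled from a larger population, where two draws say little about how modalities vary. The SAP rules that reading out. For two fixed modalities and about 180 pairs, the mean difference is estimated precisely, and the uncertainty should reflect only the sampling of participants.

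At stake is the Part A conclusion. A scale with a moderate, well-estimated offset could be declared unacceptable although its true absolute agreement exceeds 0.70. Protocol 9.2 would not have revealed this, because it assumes similar means.

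**Working it through.** **Inputs.** n = 180, SDs 8 and 9, correlation r = 0.80 and a 0.70 threshold (Protocol 9.2, SAP 6.5). Shift 0.1 SD (Protocol 2.2.2). Larger shifts and r of 0.85 to 0.95 are assumptions, shown as a range. The average variance is (64 + 81)/2 = 72.5, so 1 SD is about 8.5 points: 0.1 SD = 0.85 and 0.2 SD = 1.7 points.

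**Formulas.** With k = 2 and mean squares MSR (participants), MSC (modality) and MSE (error), the assumed standard interval is:

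- ICC(A,1) = (MSR − MSE) / (MSR + MSE + (2/n)(MSC − MSE))
- a = k·ICC / (n(1 − ICC)); b = 1 + k·ICC·(n − 1) / (n(1 − ICC))
- v = (a·MSC + b·MSE)² / [(a·MSC)²/(k − 1) + (b·MSE)²/((n − 1)(k − 1))]
- L = n(MSR − F·MSE) / [F(k·MSC + (kn − k − n)MSE) + n·MSR], with F the 97.5% point on (n − 1, v) df

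**Reproducing the plan.** Simulated bivariate normal pairs at zero shift give ICC 0.793, interval 0.732 to 0.841 and power 82%, against the stated 0.793, 0.732 to 0.841 and about 81%. This does not prove that the cited table is this interval, because other intervals give almost the same power at zero shift.

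**Isolating the 1 df.** Take r = 0.90 and a 2.5-point shift, at expected mean squares. The covariance is 0.90 × 72 = 64.8, so MSE = 72.5 − 64.8 = 7.7, MSR = 72.5 + 64.8 = 137.3 and MSC = 7.7 + 180 × 2.5²/2 = 570.2. Then ICC = 129.6 / (145 + 6.25) = 0.857. With a = 0.0665 and b = 12.91, a·MSC = 37.9 and b·MSE = 99.4, so v = 137.3² / (37.9² + 99.4²/179) = 12.6. The lower limit is 0.667. The same formula with v held at n − 1 = 179 gives 0.814. The degrees of freedom account for the difference.

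**Passing the 0.70 test.** The comparator is a Fisher-z interval for the concordance correlation, which treats the two modalities as fixed.

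| r | Shift, points (SD) | True ICC | Standard interval | Fixed-modality interval |
|---|---|---|---|---|
| 0.80 | 0 | 0.794 | 82% | 82% |
| 0.80 | 0.85 (0.10) | 0.791 | 75% | 78% |
| 0.80 | 1.7 (0.20) | 0.779 | 43% | 68% |
| 0.80 | 2.0 (0.23) | 0.773 | 26% | 60% |
| 0.85 | 2.5 (0.29) | 0.809 | 21% | 96% |
| 0.90 | 2.5 (0.29) | 0.857 | 31% | 100% |
| 0.90 | 3.0 (0.35) | 0.842 | 2% | 100% |

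Repeat runs differ by a point or two. A participant bootstrap agrees with the last column: 59% at r = 0.80 and 2 points, 99.7% at r = 0.90 and 3 points.

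**Ordering.** At a 3-point shift, raising r from 0.80 to 0.95 raises the true ICC from 0.748 to 0.888, yet the lower limit at expected mean squares falls from 0.551 to 0.404.

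**Direction of error.** At a true ICC of 0.70 with a 2.5-point shift, the standard interval passes 0.2% to 0.5% of the time across runs. The fixed-modality interval passes about 2.5%, the nominal rate.

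**The printed estimator.** The variance components are (MSR − MSE)/2 for participants, (MSC − MSE)/n for modality and MSE for error. Their ratio, multiplied through by 2, has 2/n on (MSC − MSE); SAP 6.5 prints 1/n. At r = 0.80 and 3 points, MSC − MSE = 180 × 9/2 = 810. The printed form gives 115.2 / (145 + 4.5) = 0.771, and the 2/n form gives 115.2 / (145 + 9) = 0.748. Bootstrapping the printed form at a true ICC of 0.70 gave false passes of about 7% at 2.5 points and 20% at 4 points, against about 2% to 3% with 2/n.

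**The case against.** The strongest objection is that the cited table is not in the documents, so the 1-df claim rests on an assumption about which interval it contains. That stands. Protocol 9.4.2 does tie the interval to the model's mean squares, and a two-level modality has 1 df there, but the exact formula cannot be confirmed.

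A reader might infer that any small VTC shift collapses the lower limit. The documents do not support that. At 0.1 SD and r = 0.80 the mean limit moves only from about 0.732 to 0.724, and at r = 0.85 or above it stays at 0.786 or more. Even at 1.5 points (0.18 SD), r of 0.85 or more still passes at least 93% of the time. Protocol 2.2.2 also cites studies finding no difference for MMSE or ADAS-Cog13, although it reports one study in which VTC overstated impairment in more impaired patients, without giving a size.

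Part of the fall is intended, since absolute agreement penalises a shift. That penalty is already in the true ICC and in the comparator column; the gap between the columns is not part of it.

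Finally, ICC(C,1) (SAP 6.5, Protocol 9.4.4) and the modality contrasts in SAP 6.6 would make an offset visible. They would, but neither enters the 0.70 decision.

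**Conclusion.** The concern holds for moderate shifts, on the assumption that the tabled interval is the standard Satterthwaite one. At the documents' own 0.1 SD, the interval costs about 3 points of power. From about 0.2 SD it matters: 43% against 68% passing under the plan's own correlation. For assumed correlations of 0.85 to 0.90 and shifts of 2.5 to 3 points, it mostly fails scales whose true ICC is 0.81 to 0.86.

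Three limits apply. Under the plan's correlation of 0.80, the limit at expected mean squares crosses 0.70 at about 1.6 points, where the true ICC is 0.78; failure with a true ICC above 0.80 therefore needs an assumed higher correlation. The error is conservative, so this interval does not make it easier to validate VTC wrongly. Only ADAS-Cog13 has SDs in the documents, so a reader should not infer that the same sizes are shown for ADCS-ADL, MMSE or CDR-SB. The calculation also omits the covariates and the time effect; modality keeps 1 df either way.

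The stated 81% power should be read as holding only for near-equal means.

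**What to change.** In SAP 6.5:

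- Keep ICC(A,1) and the 0.70 criterion.
- Correct the ICC(A,1) formula to 2/n on (MS_modality − MS_error). This must accompany the next step, because bootstrapping the printed formula would make the test anti-conservative.
- Replace the tabled interval for ICC(A,1) with a participant-level bootstrap 95% interval of the corrected estimator, resampling whole pairs and refitting the stated model each time. A Fisher-z interval for the concordance correlation can serve as an unadjusted check.
- Keep the tabled interval for ICC(C,1), which has no modality term.
- Restate power with the new interval at shifts of 0, 0.1 and 0.2 SD.

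The cost is SAP wording and slightly more computation, with no new data or participants. The stated power will look less favourable once a shift is allowed: with the Fisher-z interval at r = 0.80 it is about 82%, 78% and 68% at those three shifts.
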